5. SELECTION AND WITHDRAWAL OF PARTICIPANTS

5.1 Number and source of participants

Approximately 32 participants will be recruited to this study in total (approximately 24 Japanese and 8 NJNEA healthy adult male and female participants). Japanese participants will be randomized to treatment groups 1-3, NJNEA participants will be allocated to group 4.

- Treatment group 1 (Japanese N=8): UPB-101 [REDACTED] mg
- Treatment group 2 (Japanese N=8): UPB-101 [REDACTED] mg
- Treatment group 3 (Japanese N=8): UPB-101 [REDACTED] mg
- Treatment group 4 (NJNEA N=8): UPB-101 [REDACTED] mg

5.2 Replacement participants

Additional participants may be recruited to replace any withdrawn participants, in order to ensure that 32 participants complete the study. Replacement participants may be enrolled as described in Table 6 – Adaptive protocol features.

5.3 Inclusion criteria

Participants must meet all of the following criteria to be eligible for enrolment in this study:

1. Ability to provide written, personally signed, and dated informed consent to participate in the study, in accordance with the ICH Good Clinical Practice (GCP) Guideline E6 (R2) (2016) and applicable regulations, before completing any study-related procedures.
2. An understanding, ability, and willingness to fully comply with study procedures and restrictions.
3. Male or female, aged ≥18 to ≤40 years at the date of signing informed consent.
4. Participants must have a BMI between 18.0 kg/m² - 25.0 kg/m² (inclusive) at Screening and Day -1.
5. For Japanese (treatment groups 1, 2 and 3), participants must be:
 - a. Born in Japan, holding a Japanese passport,

- b. Not living outside Japan for more than 5 years at the date of signing informed consent,
- c. Have all 4 grandparents Japanese.

For NJNEA treatment group 4, participants must be:

- d. Non-Japanese
- e. Non-East Asian (Chinese, Korean, Mongolian or Taiwanese).

6. Healthy as defined by:

- a. The absence of clinically significant illness and surgery within 4 weeks prior to dosing.
- b. The absence of clinically significant history of neurological, endocrine, cardiovascular, respiratory, haematological, immunological, psychiatric, gastrointestinal, renal, hepatic, and metabolic disease.

As assessed by the Investigator, and that may confound the results of the study, pose an additional risk to the participant by study participation or affect the action, absorption, or disposition of UPB-101.

- 7. Satisfactory medical assessment with no clinically significant or relevant abnormalities as determined by medical history, physical examination, vital signs, 12-lead ECG and clinical laboratory evaluation (haematology, biochemistry, coagulation, and urinalysis) that could interfere with the participant's participation in or ability to complete the study as assessed by the Investigator.
- 8. Participants must agree to following the highly effective contraceptive requirements for the applicable duration, as described in Section 5.5.1.
- 9. Participants must agree not to donate sperm or ova from the time of the administration of study medication until 120 days later.

5.4 Exclusion criteria

Participants will be excluded from enrolment in this study if they meet any of the following criteria:

- 1. Participant has evidence of active proven or suspected bacterial, viral (including COVID-19), fungal or parasitic infections within the past 4 weeks prior to Screening (e.g., sinusitis, common cold, viral syndrome, flu-like symptoms).
- 2. Participant has a history compatible with or diagnosis of a parasitic infection and has not been treated or has not responded to standard of care therapy.
- 3. Participant has a history of malignancy of any type, other than treated *in situ* cervical cancer or surgically excised non-melanomatous skin cancers, within 5 years before Screening.
- 4. History of significant allergic reaction (anaphylaxis, angioedema) to any product (food, pharmaceutical, etc).

5. The history or presence of any of the following cardiac conditions: known structural cardiac abnormalities; family history of long QT syndrome; cardiac syncope or recurrent, idiopathic syncope; exercise-related clinically significant cardiac events.
6. Any clinically significant abnormalities in rhythm, conduction or morphology of resting ECG or clinically important abnormalities that may interfere with the interpretation of QTc interval changes. This includes participants with any of the following (at Screening or Day -1):
 - Sinus node dysfunction.
 - Clinically significant PR (PQ) interval prolongation.
 - Intermittent second- or third-degree AV block.
 - Complete bundle branch block.
 - Sustained cardiac arrhythmias including (but not limited to) atrial fibrillation or supraventricular tachycardia; any symptomatic arrhythmia with the exception of isolated extra systoles.
 - Abnormal T wave morphology which may impact on the QT/QTc assessment.
 - QT interval corrected using the Fridericia's formula (QTcF) > 450 ms (males and females).
 - Any other ECG abnormalities in the standard 12-lead ECG and 24-hour 12-lead Holter ECG or an equivalent assessment which in the opinion of the Investigator will interfere with the ECG analysis, including pacemakers.

Participants with borderline abnormalities may be included at the discretion of the PI (if the deviations are considered not to be clinically significant or their inclusion in the study does not pose a risk to the participant's health or the integrity of the study).

7. Has vital signs consistently outside of the following normal range at Screening or Day -1. Acceptable normal range is as follows:
 - supine HR 40 - 90 bpm (after at least five minutes of supine rest)
 - supine blood pressure (after at least five minutes of supine rest):

systolic blood pressure: 90 - 130 mmHg

diastolic blood pressure: 40 - 90 mmHg
8. Positive test for Hepatitis B surface antigen (HBsAg and/or Hep B core), Hepatitis C antibody (HCV Ab), or human immunodeficiency virus antibody (HIV Ab) at Screening or has a positive QuantiFERON® tuberculosis Gold (QFT-G) test for tuberculosis at Screening. Participants with an indeterminate QFT-G test may be re-tested; if a re-test remains indeterminant or is positive, the Participant will be excluded.

9. Has Total Bilirubin, ALT or AST consistently > ULN at Screening or Day -1 (up to two repeats may be taken; participant may be included if two out of the three total results are \leq ULN).
10. Participant has an estimated glomerular filtration rate (eGFR) of <80 mL/min/1.73 m² using the Chronic Kidney Disease Epidemiology Collaboration equation at Screening or Day -1 (up to two repeats may be taken; participant may be included if 2 out of the 3 total results are ≥ 80 mL/min/1.73 m²).
11. Any other abnormal findings on vital signs, ECG, physical examination or laboratory evaluation of blood and urine samples that the Investigator judges as likely to interfere with the study or pose an additional risk in participating.
12. Any other significant disease or disorder which, in the opinion of the Investigator, may either put the participant at risk because of participation in the study may influence the result of the study, or the participant's ability to participate in the study.
13. Female participants who are pregnant (including a positive serum pregnancy test at Screening or on Day -1) or breastfeeding.
14. Positive test results for alcohol or drugs of abuse (including cotinine) at Screening or Day -1.
15. History or clinical evidence of substance and/or alcohol abuse within the 2 years before Screening. Alcohol abuse is defined as regular weekly intake of more than 14 units (for both males and females), using the following NHS alcohol tracker <https://www.nhs.uk/oneyou/for-your-body/drink-less/know-your-alcohol-units/>
16. Use of tobacco in any form (e.g., smoking or chewing) or other nicotine-containing products in any form (e.g., gum, patch, electronic cigarettes) within 3 months prior to the planned first day of dosing.
17. Has used any of the following:
 - a. prescription medication (excluding female hormonal contraception or replacement therapy) within 14 days or 5 half-lives of the drug (whichever is longer), OR
 - b. over-the-counter medication (including multivitamin, herbal, or homeopathic preparations; excluding paracetamol - up to 2g paracetamol per day permitted) during the 7 days or 5 half-lives of the drug (whichever is longer), OR
 - c. Consumption of herbal remedies or dietary supplements containing St. John's Wort during the 3 weeks prior to Day 1, that the Investigator judges is likely to interfere with the study or pose an additional risk in participating.

18. Participants who have received or are planning on receiving a vaccination (including COVID-19) within 4 weeks prior to Day 1.
19. Previous exposure to UPB-101, or known or suspected intolerance or hypersensitivity to UPB-101, any closely related compound, or any of the stated ingredients.
20. Treatment with an investigational drug within 90 days or 5 half-lives preceding the first dose of study medication (or as determined by the local requirement, whichever is the longer).
21. Participant has received an antibody or therapeutic biologic product during the 6 months prior to planned date of study administration.
22. Donation of blood or blood products within 90 days prior to study medication administration, or experienced loss of blood ≥ 500 mL within 8 weeks of Screening.
23. Has a mental incapacity or language barriers precluding adequate understanding, co-operation, and compliance with the study requirements.
24. An inability to follow a standardized diet and meal schedule, as required during the study.
25. Participants with veins on either arm that are unsuitable for intravenous puncture or cannulation (e.g., veins that are difficult to locate, or a tendency to rupture during puncture).
26. Prior screen failure (where the cause of the screen failure is not deemed to be temporary), randomization, participation, or enrolment in this study. Participants who initially failed due to temporary non-medically significant issues are eligible for re-screening once the cause has resolved.

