Reproductive and gynaecological system	1) [REDACTED] [REDACTED] 2) The effects of UPB-101 on fertility, pregnancy and lactation have not been investigated and remain unknown.	1) Specific contraceptive requirements will be in place for participants and will be used in inclusion criteria (see 5.5.1). 2) Female participants will need evidence of negative pregnancy tests during Screening and prior to dosing. 3) Participants who are pregnant or breastfeeding will be excluded. 4) Participant welfare will continue to be monitored from signing of consent through to final follow up visit, with scheduled and, if necessary, unscheduled Adverse Event checks.

Target System	Effect	Risk Mitigation
Immune system	
1) [REDACTED]
 
2) [REDACTED]
 
3) [REDACTED]
	
1) Standard monitoring as with all early phase studies.
 
2) Participants will remain in unit until Day 15, in a clean and hygienic environment. This allows for close observation and reduces the risk of contracting an infection.
 
3) Participant welfare will continue to be monitored from signing of consent through to final follow up visit, with scheduled and, if necessary, unscheduled AE checks and safety assessments.
 
4) Participants with a history of any of the following will be excluded from the study:
 
 • Previous exposure or current infection with hepatitis B, hepatitis C or tuberculosis (TB). • HIV. • Evidence of active or suspected bacterial, viral, fungal or parasitic infections within the past 4 weeks prior to Screening. • History compatible with or diagnosis of a parasitic infection and has not been treated or has not responded to standard of care therapy.
	
2) [REDACTED]
 
3) [REDACTED]
	
1) All clinical staff trained to diagnose and manage potential systemic inflammatory response.
 
2) The management algorithm for systemic inflammatory response will be included in the SOM.
 
3) UPB-101 will be administered in the in-house setting with close monitoring for reactions and a mandatory period of 'on the ward' supervision by ALS qualified staff for 4 hours post-dose, including assessment of vital signs, ECG, injection site reactions and adverse events.

	
3) [REDACTED]
	
1) 12 weeks of immunogenicity follow up post-dose.

Target System	Effect	Risk Mitigation

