	4) Allergic reaction	
Participants with a history of significant allergic reaction or anaphylaxis to any substance will be excluded from this study.All clinical staff trained to diagnose and manage potential allergic reaction.UPB-101 will be administered in the in-patient setting with close monitoring for allergic reactions and a mandatory period of 'on the ward' supervision by ALS qualified staff for 4 hours post-dose, including assessment of vital signs, ECG, injection site reactions and adverse events.
Effects of a biologic compound	1) PK The PK of biologics are well understood. They have a low volume of distribution, and do not undergo liver metabolism and therefore do not generate toxic metabolites.	
Standard monitoring as with all early phase studies
Class effects (TSLPR inhibitor)	1) Infection As a TSLPR inhibitor, UPB-101 has a theoretical increased risk of infection	
Risk mitigation against class effects is described in the Immune System / Infection Risk section above

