3. STUDY DESIGN

3.1 Overall study design

This is a randomized, open-label, parallel-group, pharmacokinetic study comparing the pharmacokinetics and safety of a single dose of UPB-101 in healthy Japanese and NJNEA adults. Japanese participants must have been born in Japan, with parents and grandparents born in Japan and lived for < 5 years outside of Japan.

Each participant will receive verbal and written information about the study, followed by signing of the Informed Consent Form (ICF) prior to any Screening procedures taking place. Following signing of the informed consent, participants will be evaluated for eligibility during the Screening Days -21 to -2. Participants who are eligible at the end of the Screening assessments will be admitted on Day -1 for confirmation of eligibility, then dosed on Day 1, and discharged on Day 15. All assessments performed during the study are detailed in the study Schedule of Assessments (Table 4 and Table 5). The study will be conducted at a single site in the UK.

Table 3: Planned treatment groups

Planned Treatment Groups	Participant Ethnicity (N Participants)	Treatment	Number of Injections to Achieve Dose	Number of Doses
1	Japanese (8)	UPB-101 [REDACTED] mg SC	[REDACTED]	Single dose
2	Japanese (8)	UPB-101 [REDACTED] mg SC	[REDACTED]	
3	Japanese (8)	UPB-101 [REDACTED] mg SC	[REDACTED]	
4	Non-Japanese Non-East Asian (8)	UPB-101 [REDACTED] mg SC	[REDACTED]	

The study consists of 4 treatment groups. Three (3) treatment groups will include Japanese healthy adult volunteers and 1 treatment group will include NJNEA healthy adult volunteers.

The 4 treatment groups will be assigned as few cohorts as operationally feasible to avoid period bias, and each cohort will attempt to contain at least two participants from each treatment group.

Each participant will receive one of the following dosing regimens in parallel:

- Treatment group 1 – 1 SC dose of [REDACTED] mg of UPB-101
- Treatment group 2 – 1 SC dose of [REDACTED] mg of UPB-101
- Treatment group 3 – 1 SC dose of [REDACTED] mg of UPB-101
- Treatment group 4 - 1 SC dose of [REDACTED] mg of UPB-101

Screening

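### Exclusion criterion 1 and Table 2 count the 4-week infection look-back from Screening, so the rule is silent on minor or suspected infections in the 2 to 21 days before dosing

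*Protocol*

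**What the plan says.** Exclusion criterion 1 (Protocol Section 5.4) bars people with proven or suspected infection, naming bacterial and viral infection (COVID-19 included) together with "fungal or parasitic infections within the past 4 weeks prior to Screening". Its examples are mild illnesses: "e.g., sinusitis, common cold, viral syndrome, flu-like symptoms". Table 2 (Section 1.2.2.2) lists the same exclusion among its immune-system mitigations, with the same anchor: "Evidence of active or suspected bacterial, viral, fungal or parasitic infections within the past 4 weeks prior to Screening". The same table gives the reason for caution: "As a TSLPR inhibitor, UPB-101 has a theoretical increased risk of infection".

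On timing, Section 3.1 states that "participants will be evaluated for eligibility during the Screening Days -21 to -2". Participants are then admitted on Day -1 to confirm eligibility and dosed on Day 1.

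Two comparable 4-week rules count from a different point. Inclusion 6a (Section 5.3) requires "The absence of clinically significant illness and surgery within 4 weeks prior to dosing". Exclusion 18 concerns "a vaccination (including COVID-19) within 4 weeks prior to Day 1". The synopsis, in its main exclusion criteria, lists recent infection and untreated or unresolved infection without tying either to Screening.

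**The concern.** A look-back that ends at Screening leaves an interval before dosing that the rule does not address, and that interval is the one closest to drug exposure. Read literally, criterion 1 orders infections the wrong way round. For someone screened on Day -21, a cold on Day -25 excludes, while the same cold on Day -8 does not fall under the criterion. The protocol gives no reason for this.

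The criterion is a listed protection against a named class risk, and it precedes a single dose that cannot be withdrawn once given. A recent infection could also disturb the pre-dose white-cell or CRP values from which changes are calculated, in groups of only 8 participants.

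**Working it through.** The plan states no figure for this interval, so there is none to reproduce. The check is day arithmetic followed by a comparison of the criteria.

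**Inputs.** Criterion 1 look-back: 4 weeks = 28 days before Screening (Section 5.4). Screening: Day -21 to Day -2; dosing: Day 1 (Section 3.1). Inclusion 6a look-back: 28 days before dosing (Section 5.3). There is no Day 0, so Day -k is k days before dosing.

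**Formulae.** For Screening on Day -k:
- criterion 1 covers from k + 28 to k days before dosing;
- the interval it leaves open is the last k days;
- the part of that interval outside the 6a window is max(0, k - 28).

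| Screening | Criterion 1 covers (days before dosing) | Left open by criterion 1 | Part of that outside 6a |
|---|---|---|---|
| Day -21 | 49 to 21 | 21 days | 0 |
| Day -14 | 42 to 14 | 14 days | 0 |
| Day -7 | 35 to 7 | 7 days | 0 |
| Day -2 | 30 to 2 | 2 days | 0 |

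The gap therefore runs from 2 to 21 days and always lies inside the 6a window. If criterion 1 counted from dosing, the gap would be 0 whatever the Screening day.

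**What 6a catches and what it does not.** The two criteria share time in the gap but not scope. Criterion 1 has no significance threshold: suspected infection is enough, and a common cold is an example. Inclusion 6a applies only to clinically significant illness, and inclusion 6 is qualified by "As assessed by the Investigator, and that may confound the results of the study, pose an additional risk to the participant by study participation". Taking each possible case in the gap:
- Clinically significant infection: excluded by 6a.
- Minor or suspected infection that the Investigator judges not clinically significant: no explicit exclusion applies. In the 28 days before Screening, the same infection would exclude under criterion 1.

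**Later checks.** Table 4 schedules an update of the eligibility criteria on Day -1, and Section 3.1 places a final decision on Day 1. Both apply the criteria as written, so criterion 1 re-read on Day -1 still refers to the period before Screening.

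**The case against.** A reader might infer that an infection in the three weeks before dosing is simply not excluded. The documents do not support that. Inclusion 6a covers any clinically significant illness throughout the gap, and the qualifier to inclusion 6 is directed at the harms of concern: confounded results and added risk to the participant. Other cover exists. Inclusion 7 requires a satisfactory medical assessment; exclusions 11 and 12 allow exclusion on judgement; vital signs (with temperature) and safety bloods are repeated on Day -1; COVID-19 testing follows site procedures; and the pre-dose limits on prescription and over-the-counter medicines should bring many treated infections to light, paracetamol apart. All of this stands, and it confines the point to infections judged minor. It does not remove the point, because these provisions rest on judgement or on detectable signs, whereas criterion 1 is a fixed rule that names such mild infections.

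A second tempting inference is that the gap seriously damages safety attribution. That too is weaker than it looks. SAP Section 4.10.1 counts an event as treatment-emergent only if it starts after dosing begins, and Protocol Section 7.1 records clinically relevant pre-dose observations as medical history. An infection still incubating has no symptoms, so no look-back, however anchored, would find it. One participant in a group of 8 is 1/8 = 12.5 percentage points, but that holds for any event, and the documents give no frequency for infections in the gap. What stands is a possible disturbance of an individual's baseline laboratory values.

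Nor is criterion 1 the only short window tied to Screening: the blood-loss limit in criterion 22 (8 weeks) is too. The inconsistency is with the closest comparators, the two 4-week rules in 6a and criterion 18.

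**Conclusion.** The concern holds in a narrow form. Criterion 1 and its Table 2 counterpart leave 2 to 21 days before dosing outside the fixed infection rule. This is out of line with 6a, with criterion 18 and with the intent shown in the synopsis, which gives no window of its own. The practical gap is limited to minor or suspected infections judged not clinically significant.

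This rests on reading Screening as the participant's own screening day within Day -21 to Day -2, and on applying criterion 1 as written. How many participants would be affected cannot be estimated from the documents. Sample size and the PK analysis are unaffected. Severity is minor: a wording inconsistency in a listed safeguard that is worth correcting because doing so is easy.

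**What to change.** The sponsor should reconcile the anchor of criterion 1 and of the Table 2 bullet with inclusion 6a, criterion 18 and the synopsis, so that the infection exclusion also covers the interval from Screening to dosing. The revised wording should be applied at the Day -1 eligibility update already in Table 4, so no new visit is needed.

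The cost is a wording change in two places and probably a few more exclusions at Day -1. Reserve participants are already foreseen (Protocol Section 11.1), and criterion 26 allows re-screening after a temporary cause of failure that is not medically significant has resolved. Between them these should absorb the losses.

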5.5 Participant restrictions

Participants will have to comply with the restrictions described in Table 11. Participants must also comply with the latest COVID-19 safety measures/ testing applicable at the site at that time, for entry into the unit and during in-house stays.

Table 11: Participant restrictions

Items participants must not consume or do	When participants must stop	When participants can re-start
Tobacco in any form (e.g., smoking or chewing) or other nicotine-containing products in any form (e.g., gum, patch, electronic cigarettes)	From three months prior to the planned first day of dosing.	After study completion/last visit.
Meals/snacks/water	Whenever participants are confined in the ward, only the drinks and meals provided by	After discharge from the unit.

Items participants must not consume or do	When participants must stop	When participants can re-start
	the study personnel will be allowed. Standard meals will be provided at the standard unit times as stated in the study schedule, and meals should be completed each time.	
Caffeine-containing or Xanthine-containing products	48 hours before the planned study drug administration and each out-patient/ follow-up visit.	After study completion/last visit.
Energy drinks or drinks containing taurine, glucuronolactone (e.g., Red Bull)	48 hours before the planned study drug administration and each out-patient/ follow-up visit.	After study completion/last visit.
Alcohol	48 hours before the planned study drug administration and each out-patient/ follow-up visit.	After study completion/last visit.
Strenuous physical activity	48 hours before Screening, admission and out-patient/follow-up visit. Participants should not start new physical training activities during the study.	After study completion/last visit.
Any prescription medication. For details, including exceptions see Section 5.4 Exclusion Criteria, and Section 6.3 Concomitant Medications.	14 days or 5 half-lives (whichever is longer) before the planned study drug administration.	After study completion/last visit. If participants have a medical need to take any medication or have any medications prescribed to them by a doctor, they should follow the medical advice but inform the Investigator as soon as possible afterwards. Participants should be informed not to stop taking any medication that has been prescribed by their General Practitioner or other doctor.
Any over-the-counter medication. For details, including exceptions, see Section 6.3.	7 days or 5 half-lives (whichever is longer) before the planned study drug administration.	
Any herbal remedy or dietary supplement containing a herbal remedy.	3 weeks before the planned study drug administration.	After study completion/last visit.
Blood and plasma donation.	90 days prior to the planned study drug administration.	3 months after study completion/last visit.
Contraception: Participants must follow the contraceptive requirements as stated in Section 5.5.1.	Start times for contraceptives vary according to method used - see applicable contraceptive method in Section 5.5.1.	See specific contraception criteria in Section 5.5.1.
COVID-19 vaccination.	4 weeks before the planned first study drug administration.	After study completion / last visit.

